**2019-8-15**

**Study Background**

Fumarate hydratase (FH)-deficient renal cell carcinoma (RCC) is a kind of autosomal dominant diseases featured by FH gene mutation [1]. Since FH-deficient RCC not only demonstrates distinct genetic alteration patterns and also shows a very aggressive clinical pattern, WHO/ISUP has redefined it as a RCC subtype (it was once classified into papillary RCC (pRCC)) [2]. FH-deficient RCC patients are likely to develop metastasis at the early phase, and they also response poorly to common targeted drugs in RCC. In another words, there is no standard therapy for FH-deficient RCC.

Loss-of-function mutation of FH results in accumulation of fumarate, impairment of oxidative phosphorylation, alteration of metabolic state, and stabilization of hypoxia-inducible factor (HIF)-1 $\alpha$ , ultimately leading to the activation of angiogenic and oxidative stress response pathways [3-5]. Evidence suggests that accumulated fumarate also diminishes AMPK levels and consequent activation of mTOR and downstream pathway. Although there are current results of clinical trials (NCT01130519 and NCT01399918) suggesting the use of bevacizumab plus erlotinib or everolimus as standard

treatment for FH-deficient RCC [6, 7]. However, we retrospectively analyzed eight confirmed FH-deficient RCC in our center between 2010-2018 and found that most (7/8, 87.5%) of them did not respond well to targeted therapy (TKIs and/or mTOR inhibitors).

To date, effective treatments for FH-deficient RCC remain a major unmet clinical need. Unlike three other subtypes of RCC, including clear cell RCC (ccRCC), pRCC and chromophobe RCC (chRCC), the genomic landscape of HLRCC has not yet been reported. Without any genomic information, it is challenging to develop targeted therapy and clinical trials for FH-deficient RCC. We previously performed a Whole-exosome sequencing on FH-deficient RCC cases confirmed at our center and found that it harbored high rate of microsatellite instability (MSI), high PD-L1 positive rate. Consequently, we concluded that these patients might be sensitive to immunotherapy.

Currently numerous studies have shown that immunotherapy might be an important tool in RCC treatment [8-10], while first-line PD-1/PD-L1 inhibitors showed an merely 20%-30% overall response rate and a similar progression-free survival to that of targeted therapy. Considering the possible crosstalk between antiangiogenic therapy and tumor immune microenvironment, the immunogenicity of FH-deficient RCC could hinder the efficacy of TKI monotherapy, which indicates that combination of immunotherapy and TKI might be a potential way. Therefore, we intend to perform this clinical trial.

## **Protocol**

Study Type: Interventional

Primary Purpose: Treatment

Study Phase: Phase 2

Interventional Study Model: Single Group Assignment

Number of Arms: 1

Masking: None (Open Label)

Allocation: N/A

Enrollment: 20 [Anticipated]

Experimental: Sintilimab injection combined with Inlyta (Sintilimab injection 10ml: 100mg, 200mg intravenously, once every three weeks. Course of treatment: discontinue medication when the disease progresses clinically or radiologically. Inlyta 5mg orally, twice a day. Course of treatment: continue treatment as long as a clinical benefit is observed, or until an unacceptable toxicity is present that cannot be controlled by combination or dose adjustment.)

In the whole research process, if the disease progresses, the attending doctor has the right to carefully choose other anti-tumor methods, including radiotherapy, chemotherapy and other targeted drugs

#### Outcome Measures

Primary Outcome Measure:

1. PFS: progression-free survival

[Time Frame: 3 years]

2. ORR: objective response rate

[Time Frame: 3 years]

Secondary Outcome Measure:

3. OS: overall survival

[Time Frame: 3 years]

4. life quality: evaluate life quality

[Time Frame: 3 years]

Other Pre-specified Outcome Measures:

5. drug related adverse effect

[Time Frame: 3 years]

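### Do two unranked primary outcomes in one arm of 20, with several response figures in the background, leave the trial without a usable yardstick?

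*Protocol*

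**What the plan says.** Under Outcome Measures, "PFS: progression-free survival" and "ORR: objective response rate" are items 1 and 2 of the primary list, each with a three-year time frame. The numbering runs on through the secondary and other outcomes to 5, so it is a list index and not a ranking.

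The Protocol section gives "Interventional Study Model: Single Group Assignment" and "Enrollment: 20 [Anticipated". No alpha, power, null rate, target rate or decision rule accompanies the 20.

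The Study Background mentions earlier results in three places:

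- On the centre's own eight FH-deficient cases: "most (7/8, 87.5%) of them did not respond well to targeted therapy (TKIs and/or mTOR inhibitors".
- On RCC in general: "first-line PD-1/PD-L1 inhibitors showed an merely 20%-30% overall response rate", with PFS described only as similar to that on targeted therapy and no number given.
- On existing treatment: "there is no standard therapy for FH-deficient RCC", and then other trials "suggesting the use of bevacizumab plus erlotinib or everolimus as standard" treatment, without figures.

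**The concern.** With no control arm, any statement that the combination beats existing treatment has to borrow a value from outside the trial. The background seems to supply several, and they differ. If 7 of 8 poor responses is read as a response rate of 1/8, or 12.5%, a modest result looks like success. Against 30% the same result does not. PFS has no number to be read against at all.

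In an open-label trial with two unranked primaries, the sponsor could then pair the more favourable outcome with the more favourable benchmark once the results are known. The two remarks on standard therapy add to the impression that the comparator is unsettled.

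**Working it through.** **Inputs.** From the protocol: n = 20, one arm; 7/8 poor responses; 20% to 30%. Not in the protocol, so assumed: an exact binomial test, one-sided alpha of 0.05 (0.025 and 0.10 also shown), and true ORRs of 30%, 40% and 50%. There is no design calculation to reproduce, because the 20 comes without any.

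**Step 1: the bar for each candidate rate.** The bar is the smallest r with P(X ≥ r | n = 20, p0) ≤ alpha.

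| p0 | Bar at 0.05 | P at bar | P at one fewer | Power at true ORR 40% | Bar at 0.025 | Bar at 0.10 |
|---|---|---|---|---|---|---|
| 12.5% | 6/20 | 0.0312 | 0.0950 | 0.874 | 7/20 | 5/20 |
| 20% | 8/20 | 0.0321 | 0.0867 | 0.584 | 9/20 | 7/20 |
| 30% | 10/20 | 0.0480 | 0.1133 | 0.245 | 11/20 | 10/20 |

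The arithmetic is sound. At 0.05, a count of 6 to 9 clears the lowest bar but not the highest, with probability 0.536, 0.630 and 0.391 at true ORRs of 30%, 40% and 50%. But every entry needs an alpha and a null that the protocol does not state.

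**Step 2: can 12.5% serve as a null?** The protocol describes patients who fared poorly on targeted treatment; it does not report objective responses. Taking the complement, 1/8, is the reader's own step. Even then the exact 95% CI for 1/8 is 0.3% to 52.7%. If the eight cases are treated as a sample and not as a known constant, a one-sided Fisher test gives p = 0.077 at 10/20 and p = 0.048 at 11/20. The bar against that series would then be 11/20, above the one for 30%. The low end of the range, 6/20, exists only if eight loosely described cases are taken as an exact rate.

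**Step 3: what is left without it.** The bars run from 8/20 to 10/20, which reflects the width of one quoted interval, 20% to 30%. The chance of 8 or 9 responders at a true ORR of 40% is 0.584 − 0.245 = 0.339, against 0.630 for 6 to 9.

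**Step 4: do the background figures conflict?**

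| | Centre series | General RCC figure |
|---|---|---|
| Disease | FH-deficient RCC | RCC generally |
| Treatment | TKI and/or mTOR inhibitor | PD-1/PD-L1 inhibitor, first line |
| Measure | informal description | overall response rate |

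Disease, treatment and measure all differ, so both can be true. Together they form one rationale: targeted treatment did poorly in this disease, checkpoint inhibition alone does modestly in RCC, so try the combination. Neither is named as a value for the primary analysis.

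The two remarks on standard therapy are a concession followed by a rebuttal: other trials have proposed regimens, but the centre's cases did badly. The rebuttal may be thin, since the description of the eight cases names no bevacizumab. That is a criticism of the introduction and changes nothing in how PFS or ORR is measured or analysed.

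**Step 5: multiplicity.** If success on either primary at 0.05 were enough, the familywise error would be at most 0.10, and 1 − 0.95² = 0.0975 under independence. That applies only under an either-or rule, and the protocol states none.

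**Step 6: precision.** The exact 95% CI for ORR is 19.1% to 63.9% at 8/20 and 31.5% to 76.9% at 11/20. If all 20 progress without censoring, the distribution-free interval for median PFS runs from the 6th to the 15th ordered time (coverage 95.9%). These widths follow from n = 20. Ranking the outcomes or naming a benchmark would not alter them.

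**The case for a change.** The strongest case for the concern is that the choice of primary outcome belongs in the protocol, that an uncontrolled trial needs an outside value for any claim of benefit, and that the spread of bars does not depend on the alpha assumed: 7 to 11 at one-sided 0.025, 5 to 10 at 0.10. One sentence, either declaring the trial estimation only or naming a deciding outcome with its threshold, would close the gap without a single extra patient.

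Part of this stands. The two primaries are unranked, no benchmark is chosen, and such a sentence would help the reader. But the choice of primary outcomes is in the protocol: there are two, both named. How they are weighed, against what value and at what level is commonly set out in the analysis plan. The sentence would record a policy; it would not change an estimate, an interval or the sample size. The worry about picking a benchmark afterwards is a worry about a claim the document does not make.

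**Conclusion.** No error. The protocol names two primary outcomes in a small uncontrolled phase 2 trial of a rare tumour, and both can be estimated and reported with intervals as they stand. The range of 6/20 to 10/20 is correct arithmetic on inputs the protocol does not contain: an assumed one-sided 5% and a reading of eight cases as a 12.5% response rate. Without that reading it shrinks to 8/20 to 10/20, the width of one quoted range. The background figures describe different treatments and populations and do not contradict each other.

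This rests on two conditions: that details such as the lead outcome, reference value and threshold may sit in an analysis plan not available here, and that no success claim is made in the protocol. If a report later declared superiority over one of these background figures without having fixed it beforehand, that claim would be open to challenge. The protocol text itself is not.

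### The only adverse-event outcome counts drug-related events; in a single-arm, open-label trial of 20 patients, list events of any cause beside it

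*Protocol*

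**What the plan says.** The Outcome Measures section of the protocol lists five items. PFS and ORR are primary, OS and quality of life are secondary, and item 5, under the other pre-specified measures, is "drug related adverse effect" with a time frame of 3 years. Item 5 is the only adverse-event outcome. The protocol text lists no outcome for adverse events of any cause, treatment-emergent events or serious events, and it does not say who judges relatedness or how. The only other toxicity wording on study treatment, in the description of the experimental regimen, is a condition for ending one of the drugs and not an outcome.

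The design fields in the Protocol section give "Number of Arms: 1", "Masking: None (Open Label") and "Enrollment: 20 [Anticipated"]. The regimen is "Sintilimab injection combined with Inlyta", so every patient is to receive both drugs. The same section says that "if the disease progresses, the attending doctor has the right to carefully choose other anti-tumor methods", "including radiotherapy, chemotherapy and other targeted drugs". The Study Background says that the disease "shows a very aggressive clinical pattern".

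**The concern.** A count of drug-related events is a count of events that have passed a causality judgement. In a randomised trial, a reader can compare all events between arms and see whether the judgements look reasonable. Here there is no second arm, and whoever makes the judgement knows that the patient is assigned to both drugs.

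The setting also makes the judgement hard. An aggressive tumour can be expected to cause events of its own, and the Eligibility section admits patients with ECOG status up to 2 and requires only that expected survival exceed 3 months. In addition, item 5 does not say which drug is meant. Treatment after progression may include chemotherapy and other targeted agents within the 3-year time frame, so an event caused by a later drug could be read as in or out.

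At stake is how far a reader can rely on the one pre-specified safety result. If only related events are shown, the number set aside by attribution cannot be seen.

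**Working it through.** The protocol states no safety rate, so there is no figure to reproduce. The check has two parts.

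**Text**

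1. Scope of the adverse-event outcome: drug-related (Outcome Measures, item 5).
2. Other adverse-event outcomes in the list: none.
3. Comparator: none. Masking: none (Protocol, design fields).
4. It follows that an event's entry into item 5 depends on attribution, and that nothing in the design gives a background rate against which to check it. A count regardless of causality does not depend on attribution.

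**Illustrative size**

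The only input is n = 20, the planned enrolment. No incidence or attribution rate is assumed.

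- Step for one reclassified patient: 1/n = 1/20 = 0.05, or 5 percentage points.
- Smallest case: a type of event occurs in exactly one patient. Exact (Clopper-Pearson) 95% limits are:
  - Judged unrelated, item 5 shows 0/20 = 0%. The lower limit is 0 and the upper limit is 1 − 0.025^(1/20) = 0.168, so the interval is 0% to 16.8%.
  - Judged related, item 5 shows 1/20 = 5%. The lower limit is 1 − 0.975^(1/20) = 0.0013. The upper limit solves (1 − p)^20 + 20p(1 − p)^19 = 0.025, giving p = 0.249. The interval is 0.1% to 24.9%.

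| Causality call | Item 5 shows | Any-cause line shows |
|---|---|---|
| Unrelated | 0/20 (0% to 16.8%) | 1/20 (0.1% to 24.9%) |
| Related | 1/20 (0.1% to 24.9%) | 1/20 (0.1% to 24.9%) |

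The call alone decides whether item 5 shows the event at all, while the any-cause line is the same either way. The two intervals overlap heavily: sampling error at n = 20 is larger than the shift from one patient. Adding the second count changes no sample size, power or significance level.

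**The case against.** The strongest objection is that tables of all adverse events by grade and seriousness are ordinary SAP content, and the SAP is not at hand. The outcome list is also terse throughout: the quality-of-life item names no instrument, and PFS and ORR are not defined there. In that style item 5 may be a topic label, and nothing in it says that other events are excluded. This stands in part. It rules out any claim that reporting of all events is missing from the trial. It does not remove the point, because the protocol itself sets the scope of the named outcome, and an SAP table would supplement that scope without changing it.

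A second objection is that each measure has a weakness: with one arm, a count of all events also contains events caused by the disease, so it does not estimate drug-caused harm. That is correct, and it is why the two counts should stand side by side and neither should replace the other. It is likewise true that the 5-point step holds for any binary outcome in 20 patients, and that OS (under its usual definition) and quality of life need no causality call. Neither of those, however, is an adverse-event outcome.

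A reader might infer that events judged unrelated will go unrecorded, or that the trial will understate harm. The protocol does not support either inference. It has no rule that limits what is collected, and it gives no rates from which understatement could be shown.

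**Conclusion.** The point holds as a modest one about the scope of a measure that is neither primary nor secondary. As written, the only adverse-event outcome rests on an unmasked causality judgement that no comparator can check. One reclassified patient moves its rate by 5 percentage points, and for an event seen in a single patient the judgement decides whether any case appears. These figures are illustrations that assume 20 patients are enrolled and form the denominator. The total effect of attribution cannot be computed from the protocol.

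PFS and ORR are unaffected. Nor does the point justify dropping the drug-related count or making it secondary to the any-cause count. The possibility of other anti-tumour treatment after progression supports stating which drugs item 5 refers to; a separate tabulation of later events would go beyond the defect described here. The point is worth considering as a cheap improvement to safety reporting.

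**What to change.** Keep item 5 and specify it as adverse events judged related to either study drug. List beside it all adverse events regardless of causality, by grade and seriousness. Readers can then see how many events attribution removed.

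The cost is a small wording change and one more safety table, with some added event recording if events judged unrelated are not already captured. The any-cause rate will be at least as high as the drug-related one, and probably higher, and it also contains disease-related events. The report should say so, so that it is not read as an estimate of harm caused by the drugs. If such reporting is already planned in the SAP, the change only brings the protocol's outcome list into line with it.

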#### **Eligibility**

Minimum Age: 18 Years

Maximum Age:

Sex: All

Gender Based:

Accepts Healthy Volunteers: No

Criteria: Inclusion Criteria:

1. age  $\geq 18$ ;

2. histology characteristics accord with FH-deficient RCC;

3. gene testing confirms germline and/or somatic FH gene mutation ;

4. ECOG (Eastern Cooperative Oncology Group) $\leq 2$ ;

5. expected survival  $>3$  months;

6. blood routine indexes: neutrophils  $\geq 1.5 \times 10^9$ , platelets  $\geq 100 \times 10^9$ , hemoglobin  $\geq 90$ g/L;

7. liver function: bilirubin  $\leq$  normal upper limit 1.5 times, AST  $\leq$  normal upper limit 2.5 times; Serum creatinine  $\leq 1.5$  times of normal upper limit; Serum calcium concentration:  $\leq 12.0$  mg/dL;

8. coagulation function: PT  $\leq 1.5$  times of normal upper limit;

9. the following diseases did not appear within 12 months: myocardial infarction, severe or unstable angina pectoris, asymptomatic heart failure, cardiovascular and cerebrovascular accident or transient ischemic attack, etc.

10. all patients signed informed consent.

Exclusion Criteria:

1. other malignancies previously or at the same time that are different

from the primary site or histology of the tumor assessed in this study, except cervical carcinoma in situ, basal-cell carcinoma that has been fully treated, superficial bladder tumor (Ta, Tis, T1) or other malignancies that occurred before the enrollment and have been cured for more than 3 years;

2. renal decompensation requires hemodialysis or peritoneal dialysis;
3. arrhythmia need anti-arrhythmic treatment, symptomatic coronary artery disease or myocardial ischemia (myocardial infarction), nearly six months, or congestive heart failure than NYHA # level; Hypertension (systolic blood pressure >160 mmHg or diastolic blood pressure >100 mmHg) that has been treated with 2 or more antihypertensive treatments and still cannot be controlled;
4. severe active clinical infection;
5. patients with coagulation disorder or bleeding constitution;
6. major surgery or severe trauma was performed within 4 weeks before enrollment;
7. a history of allogeneic organ transplantation or bone marrow transplantation;
8. drug abuse and medical, psychological or social conditions that may interfere with patients' participation in research or affect the evaluation of results;
9. known or suspected allergy to the study drug;
10. those who received treatment other than this study within 4 weeks prior to and during the study period.

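### An immunotherapy-plus-TKI trial names transplantation as its only immune-related exclusion; autoimmune disease and systemic immunosuppression are reached, if at all, only through general or ambiguous wording

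*Protocol*

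**What the plan says.** The Study Background builds the case for the regimen on immune sensitivity. After reporting microsatellite instability and PD-L1 positivity in the centre's own cases, it states: "Consequently, we concluded that these patients might be sensitive to immunotherapy". It then discusses PD-1/PD-L1 inhibitors and argues that "combination of immunotherapy and TKI might be a potential way".

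The Protocol section sets out the design: "Interventional Study Model: Single Group Assignment", open label, "Enrollment: 20 [Anticipated", with the arm described as "Experimental: Sintilimab injection combined with Inlyta". ORR and PFS are both listed as primary outcomes. Drug-related adverse effects are a further pre-specified outcome.

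Four exclusion criteria under Eligibility matter here:

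- **Item 7** excludes patients with "a history of allogeneic organ transplantation or bone marrow transplantation".
- **Item 8** excludes drug abuse and also medical, psychological or social conditions that may hinder participation or "affect the evaluation of results".
- **Item 10** excludes patients given any treatment outside the study, from 4 weeks beforehand and throughout it. It does not say what kind of treatment is meant.
- **Item 3** covers cardiac disease and hypertension. Hypertension excludes only if it stays above the stated limits despite two or more antihypertensive treatments.

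**The concern.** Entry criteria should fit the mechanism under test. Here the hypothesis concerns an immune effect added to a TKI, and item 7 shows that immune status was thought relevant to entry. Two other immune-related states are nevertheless left unnamed: active autoimmune disease, and continuing systemic immunosuppressive treatment.

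Three things are at stake:

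- **Participant safety.** A patient with active autoimmune disease may be exposed to an immune-mediated risk that screening could have avoided.
- **Attribution of adverse effects.** A worsening of pre-existing autoimmune disease may be hard to tell from an effect of the study drug, and there is no control arm to show the background rate.
- **Interpretation of response.** In a patient on systemic immunosuppression, the immune part of the combination may be blunted, so a non-response is weaker evidence about the stated hypothesis.

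If the only route to exclusion is a general clause, two investigators could also decide the same case differently.

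**Working it through.** The protocol gives no figure on this point, so there is nothing to reproduce. The check is a reading of all ten inclusion and all ten exclusion criteria against the rationale.

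**1. Is either state named?** The inclusion criteria cover age, histology, FH mutation, ECOG status, expected survival, blood counts, liver function with creatinine and calcium, coagulation, recent cardiovascular events, and consent. The exclusions cover:

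1. other malignancy
2. dialysis
3. cardiac disease and uncontrolled hypertension
4. severe active infection
5. coagulation disorder or bleeding tendency
6. recent major surgery or trauma
7. transplantation
8. drug abuse and interfering conditions
9. allergy to the study drug
10. non-study treatment

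Autoimmune disease, corticosteroids, immunosuppressive drugs and immunodeficiency appear in none of the twenty. Transplantation is the only immune-related entry.

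**2. Does item 8 reach them?** It can. It includes medical conditions, and one ground is that the condition may "affect the evaluation of results". Autoimmune disease that clouds the attribution of adverse effects could fall within that wording. But the clause names no condition and gives no threshold, so whether a given patient is excluded depends on how the clause is applied.

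**3. Does item 10 reach them?** There are two readings.

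| Reading of treatment in item 10 | Ongoing systemic immunosuppression | Active autoimmune disease without treatment | Fit with item 3 |
|---|---|---|---|
| Any treatment outside the study | Excluded | Not reached | Poor: patients taking antihypertensives would be excluded already, leaving the hypertension part of item 3 with almost nothing to do |
| Anti-tumour treatment only | Not reached | Not reached | Good: patients whose blood pressure is controlled on medication can enter |

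Item 3 makes the second reading the more plausible one, but that is an inference, since item 10 does not say so. On neither reading does item 10 reach active autoimmune disease that is not being treated.

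**4. Result by state.** Active autoimmune disease: not named; reached at most by item 8. Ongoing systemic immunosuppression: not named; reached at most indirectly, by items 8 and 10. The gap is firmer for the first than for the second.

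**5. Scale, as illustration only.** With n = 20, one patient is 1/20 = 5 percentage points of ORR. Suppose k of the 20 could not respond at all and the rest respond with probability p. Expected ORR is then p × (20 − k)/20. Both k and p are assumptions; the protocol gives neither.

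| Assumed p | k = 1 | k = 2 |
|---|---|---|
| 0.30 | 0.30 × 19/20 = 28.5% | 0.30 × 18/20 = 27.0% |
| 0.50 | 0.50 × 19/20 = 47.5% | 0.50 × 18/20 = 45.0% |

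For a given k and p this is the largest loss possible, because such patients still receive Inlyta and may respond to it.

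**The case against.** The strongest reply is that the criteria already cover these patients. Item 8 extends to medical conditions that affect evaluation, and it contains no wording that leaves the matter to the investigator's opinion. Item 10, read literally, bars continuing immunosuppressive treatment outright. This has force. A reader might infer from the list that no exclusion bars such patients and that they are simply eligible. The documents do not support that inference: items 8 and 10 could each be used to refuse them. What remains is that neither item names them, that item 8 sets no threshold, and that item 10 has a literal reading at odds with item 3.

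A second reply is that the clinical premises come from outside the document. The protocol does not itself label sintilimab a PD-1 antibody, and it says nothing about autoimmune flares or about immunosuppression blunting the effect. That is correct, and these remain assumptions. The protocol does, however, present the regimen as immunotherapy plus TKI, which is enough to make immune status at entry relevant.

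A third reply concerns size. Nothing suggests how many such patients would present, and 5 percentage points is the weight of any patient in an arm of 20. This stands in full. It would also be too strong to conclude that a non-response in an immunosuppressed patient carries no information: the hypothesis concerns the combination, and the patient still receives the TKI.

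**Conclusion.** The point holds as one of incomplete and partly ambiguous eligibility wording. Screening by these criteria can admit patients with active autoimmune disease or on systemic immunosuppression, or can admit them inconsistently. The consequences are avoidable immune-mediated risk, confounded attribution of drug-related adverse effects, and a less interpretable response in an uncontrolled arm of 20.

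The size of the effect cannot be derived from the document. The ORR illustration rests on assumed values of k and p and on the extreme assumption that affected patients cannot respond; it shows scale and is not an estimate of bias. The conclusion rests on the regimen acting through the immune system, as the Study Background argues, and on item 10 being open to the narrower reading that item 3 suggests. If the sponsor confirms the literal reading of item 10, the immunosuppression half largely falls away, but item 3 would then need to be reconciled with it. The autoimmune half would remain.

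**What to change.** Add an explicit exclusion beside item 7 covering active autoimmune disease and ongoing systemic immunosuppression at entry. It should name autoimmune disease as such, since active disease without systemic treatment is the group that item 10 cannot reach on any reading. The clinical definitions and any exceptions are for the investigators to set.

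State in item 10 whether treatment means anti-tumour treatment only, so that items 3, 7, 8 and 10 agree.

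The cost is a line or two in the eligibility section and the possible loss of an occasional candidate in a rare disease. In return, screening becomes consistent, and both the adverse-effect and response results are easier to interpret.
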